7.4 Software

SAS® software version 9.4 or higher will be used to perform all statistical analyses.

8 STATISTICAL METHODS OF ANALYSES

8.1 General Principles

The efficacy analyses for PK/PD parameters will be based on PK/PD Analysis Set, other efficacy analyses (RGI-C, RSS and growth) will be based on the Efficacy Analysis Set, and safety analyses will be based on Safety Analysis Set. Descriptive statistics will be used to summarize the data. For continuous variables, the mean, standard deviation, standard error, median, interquartile range (Q1, Q3), minimum, and maximum will be provided. For discrete data, the frequency and percent distributions will be provided. Statistical tests will be two-sided at the alpha = 0.05 significance level. Two-sided 95% confidence intervals will also be presented. In general, missing data will be treated as missing and no statistical imputation method will be used unless stated otherwise. No adjustment on multiplicity will be made for statistical comparisons unless stated otherwise. All data obtained from the CRFs as well as any derived data will be included in data listings.

8.2 Subject Accountability

The number and percentage of subjects in each study population will be summarized. Screen-failure subjects and the associated reasons for failure to randomize will be tabulated. The number and percentage of subjects who complete the treatment period and of subjects who prematurely discontinue will be presented. The reasons for premature discontinuation from treatment period will be presented.

8.3 Protocol Deviations

All protocol deviations will be presented in listings.

8.4 Investigational Product Administration

The total dose administered and weight-based dose will be summarized by study visit.

8.5 Demographic and Baseline Characteristics

The following demographic parameters and baseline characteristics will be summarized descriptively for the Efficacy Analysis Set:

- Age
- Gender
- Ethnicity
- Race
- Recumbent length/standing height
- Weight
- BMI

- SOC duration, age when SOC initiated
- RSS scores
- XLH biochemical parameters
- PHEX mutation
- Renal ultrasound scores

8.6 Prior and Concomitant Medication

Prior medication is defined as any medication started before the date of the first dose of investigational product (medication start date prior to the first dose date). Concomitant medication is defined as any medication taken on or after the date of the first dose of investigational product [medication end date on or after first dose date (or ongoing), and medication start date prior or on the last dose date]. Any concomitant medications started after the date of the last dose of investigational product will not be presented in the summary tables but will be included in the subject data listings. If start date is completely missing and end date is before first dose date, the medication will be considered as prior, otherwise it will be considered as concomitant.

Both prior and concomitant medications will be coded by drug name and therapeutic class using WHODRUG version 2015Q3 or the latest version at the time of snapshot/database lock. If a subject took a specific medication multiple times or took multiple medications within a specific therapeutic class, that subject would be counted only once for the coded drug name or therapeutic class.

8.7 Medical History / XLH Medical and Family History

Medical history will be coded by MedDRA version 18.1 or the latest version at the time of snapshot/database lock. Counts and percentages of subjects with medical history will be tabulated by system organ class and preferred term. Subject level listings for the pre-existing medical conditions, XLH medical history and family history will be provided.

8.8 Efficacy Analysis

The efficacy analyses for PD parameters will be performed on PK/PD Analysis Set. The efficacy analyses for clinical endpoints (RSS, RGI-C and growth) will be performed on Efficacy Analysis Set.

8.8.1 Generalized Estimating Equations Model

By-visit analyses using the Generalized Estimating Equations (GEE) model will be presented for all efficacy parameters. The GEE model will include study visit as categorical variables. To model the covariance structure, the exchangeable covariance matrix will be selected initially. If the exchangeable covariance structure leads to non-convergence, independence covariance structure will be applied. 95% confidence intervals (CIs) and p-values will be provided for statistical significance assessment. Baseline measures will be used as covariates.

For example, baseline RSS score will be used in the modeling for change in baseline in RSS score and for RGI-C score. Age and gender may also be used as covariates in growth endpoint models.

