4.2 Secondary Efficacy Endpoints

The secondary efficacy endpoints include

- Change in rickets at Week 40 as assessed by the Radiograph Global Impression of Change (RGI-C) global score
- Change in rickets at Week 64 as assessed by RGI-C global score
- Change from baseline in Rickets Severity Score (RSS) total score at Weeks 40 and 64
- Change in lower extremity skeletal abnormalities, including genu varum and genu valgus, as determined by the RGI-C long leg score at Weeks 40 and 64
- Change in recumbent length/standing height from baseline to post-treatment study time points in cm, height-for-age z-scores, and percentiles. Historical growth records may be used to evaluate change in growth velocity
- Change and percent change from baseline over time in serum alkaline phosphatase (ALP)

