4.3 Other Efficacy Endpoints

Other efficacy endpoints include

- Change from baseline over time in serum 1,25(OH)₂D and urinary phosphorus
- Change in rickets at Week 40 and 64 as assessed by RGI-C wrist score and knee score
- Change from baseline in RSS wrist score and knee scores at Week 40 and 64

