8.8.4 Other Pharmacodynamics Parameters

Other PD parameters such as ALP, 1,25(OH)₂D and urine phosphorus will be summarized descriptively. Summary statistics will be provided for observed value, change from baseline and percentage of change from baseline at each visit. Graphic display will be provided to show the change in PD parameters over time.

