10 APPENDICES

Appendix 1: Efficacy Endpoint Summary Table

Endpoints	Scale	Analysis Set	Comparisons	Data Time Points	Week 40 Analysis	Week 64 Analysis
Serum phosphorus	Continuous	PK/PD	Baseline vs. Post-baseline	Refer to Schedule of Events (Appendix 3)	GEE Descriptive Statistics	GEE Descriptive Statistics
RGI-C wrist, knee, global and lower limb deformity scores	Continuous Categorical	Efficacy	Baseline vs. Post-baseline	Baseline, Week 40, 64	GEE Descriptive Statistics	GEE Descriptive Statistics
RSS knee, wrist and total scores	Continuous	Efficacy	Baseline vs. Post-baseline	Baseline, Week 40, 64	GEE Descriptive Statistics	GEE Descriptive Statistics
Growth (standing height/recumbent length)	Continuous	Efficacy	Baseline vs. Post-baseline	Baseline, Week 12, 24, 40, 64	GEE Descriptive Statistics	GEE Descriptive Statistics
Other PD parameters	Continuous	PK/PD	Baseline vs. Post-baseline	Refer to Schedule of Events (Appendix 3)	Descriptive Statistics	Descriptive Statistics

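### Does the GEE wording in SAP 8.8.1 leave open whether ALP, 1,25(OH)2D and urinary phosphorus are formally tested?

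*SAP*

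**What the plan says.** Section 8.8.1 describes the general model: "By-visit analyses using the Generalized Estimating Equations (GEE) model will be presented for all efficacy parameters". It attaches 95% confidence intervals and p-values to that model and names no exception.

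The endpoint lists class three biochemical markers as efficacy. Section 4.2 includes "Change and percent change from baseline over time in serum alkaline phosphatase (ALP") among the secondary endpoints. Section 4.3, which opens with "Other efficacy endpoints include", names serum 1,25(OH)2D "and urinary phosphorus". Section 8.8 also treats such markers as part of the efficacy analysis: "The efficacy analyses for PD parameters will be performed on PK/PD Analysis Set".

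The section devoted to these markers, 8.8.4, begins "Other PD parameters such as ALP", goes on to 1,25(OH)2D, and states that these and "urine phosphorus will be summarized descriptively". It asks for summaries of the observed value, change and percent change at each visit, with graphs. It mentions no GEE, interval or p-value. In Appendix 1 the row "Other PD parameters" carries descriptive statistics alone at Week 40 and Week 64. Each of the other four rows carries GEE together with descriptive statistics.

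**The concern.** Calling ALP a pharmacodynamic marker does not take it outside 8.8.1, because the SAP lists it as an efficacy endpoint and places pharmacodynamic parameters under efficacy analysis. On a literal reading, then, 8.8.1 requires a GEE with p-values for the three markers, while 8.8.4 and Appendix 1 provide none.

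The timing adds to the worry. The study is open-label, and section 3.6 plans a Week 24 administrative analysis that includes pharmacodynamic data, ahead of the primary analysis at Week 40. Testing is unadjusted for multiplicity (8.1). If the SAP really left the choice open, whether to attach p-values to a named secondary endpoint could be settled after its data had been seen, with SAP text to cite for either choice. Section 4.2 also defines ALP by both change and percent change, and 8.8.1 does not say which a model would use.

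**Working it through.** The SAP gives no figure to reproduce here, so the check is a comparison of passages.

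**Step 1: set each endpoint's class beside its assigned analysis.**

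| Endpoint | Class (section 4) | Analysis in its own section | Appendix 1 |
|---|---|---|---|
| Serum phosphorus | Primary | Descriptive and GEE (8.8.2) | GEE and descriptive |
| RGI-C | Global and long leg secondary; wrist and knee other | GEE and descriptive (8.8.3.1) | GEE and descriptive |
| RSS | Total secondary; wrist and knee other | GEE and descriptive (8.8.3.2) | GEE and descriptive |
| Height/length | Secondary, in cm, Z-score and percentile | Descriptive for all three; GEE for the Z-score (8.8.3.3) | GEE and descriptive |
| ALP | Secondary | Descriptive (8.8.4) | Descriptive |
| 1,25(OH)2D, urinary phosphorus | Other | Descriptive (8.8.4) | Descriptive |

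**Step 2: ask whether the specific passages agree.** They do. For the three markers, 8.8.4 and Appendix 1 give the same answer at both analysis times. The only text pointing the other way is the word *all* in the general paragraph.

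**Step 3: ask how 8.8.1 is used elsewhere.** Section 8.8.3.3 applies GEE to the Z-score and not to centimetres or percentiles, although 4.2 lists all three. So the endpoint sections narrow the general paragraph in a second place too. Nor does endpoint tier decide who gets GEE: wrist and knee scores are only other endpoints and have it, while ALP is secondary and does not. The dividing line is the one drawn in the endpoint sections and Appendix 1.

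**Step 4: ask whether the texts exclude each other.** Section 8.8.4 does not say that descriptive summaries are the only analysis, and 8.8.2 pairs descriptive statistics with GEE for serum phosphorus. The descriptive-only reading comes from the contrast between rows in Appendix 1. This is inconsistent scope wording, not two instructions that cannot both be carried out.

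**Step 5: size what turns on it.** Marks in the Appendix 3 schedule were counted, not placed by week, because column alignment is lost in the text at hand. The last 1,25(OH)2D, spot urine and chemistry marks in Table 10.2 are taken to be the Week 76 safety visit. Post-baseline marks, with Week 76:

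- ALP-only row: 2 + 2 − 1 = 3 (none at Week 76)
- Chemistry panel, which includes ALP (Appendix 2): 5 + 5 − 2 = 8, removing screening and baseline
- 1,25(OH)2D: 4 + 6 − 1 = 9
- Spot urine: 5 + 6 − 1 = 10

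Without Week 76 these become 3, 7, 8 and 9. The fewest model estimates at stake are 3 + 8 + 9 = 20 (ALP-only row, change only, no Week 76). The most are 8 + 9 + 10 = 27 for change, plus 8 for ALP percent change, giving 35. That upper figure assumes the panel covers the ALP-only visits. The range is wide because it depends on counting choices, and the conclusion does not rest on it.

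**The case for a change.** The strongest case for amending the plan is about ALP. It is a named secondary endpoint, yet 8.8.3, the section on secondary endpoints, covers only RGI-C, RSS and growth. ALP appears under other pharmacodynamic parameters and has no Appendix 1 row of its own, so a reader cannot tell whether leaving out inference was deliberate. No clause ranks one SAP section above another: the one in section 3 gives the protocol authority over the design overview, and those in 8.1 that allow for exceptions concern missing data and multiplicity. Because 8.8.4 does not forbid a model, p-values could be added without breaching it.

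The description is accurate, and the wording in 8.8.1 is looser than it should be. It does not follow that the analysis is undecided. Section 8.8.4 names ALP, and Appendix 1 omits GEE for that row while naming it in every other. Two agreeing entries of that kind are better evidence of intent than one word in a general paragraph, and a SAP seldom needs a clause to say so. Reporting an ALP p-value would mean going beyond both entries, which anyone comparing the report with the SAP could see. Providing for GEE on ALP would reopen a settled choice and add unadjusted p-values in about 10 subjects.

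**Conclusion.** No change follows. The inconsistency is real but clerical: 8.8.1 is worded too broadly, and 8.8.4 with Appendix 1 already settles that ALP, 1,25(OH)2D and urinary phosphorus are summarised descriptively. This rests on reading the specific entries as governing the general paragraph, which the SAP does not state but which 8.8.3.3 supports by narrowing GEE in the same way.

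If that reading were wrong, the effect would still be small. Section 8.1 includes the mean and standard error for continuous variables, and 8.8.4 asks for summaries of change and percent change by visit, so the size and precision of any ALP response are reported regardless. The SAP rests no decision rule on these p-values. The GEE for serum phosphorus, RGI-C, RSS and the height Z-score is unaffected, as is the trial's conclusion.

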3.5 Sample Size Considerations

The study will enroll approximately 10 pediatric subjects between 1 and 4 years old, inclusive, with clinical findings consistent with XLH including hypophosphatemia and radiographic evidence of rickets (at least 5 subjects will have a rickets severity score (RSS) at the knee of ≥ 1.5 points at Screening), and a confirmed *PHEX* mutation or variant of uncertain significance. To maintain a level of gender balance, no more than 7 subjects of either gender will be enrolled.

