8.8.2 Primary Efficacy Endpoint

The primary efficacy endpoint is the change from baseline over time in serum phosphorus. Descriptive statistics will be provided for observed value in serum phosphorus, change from baseline and percentage of change from baseline at each visit. The GEE model will be applied to obtain the 95% CIs and p-values. Baseline serum phosphorus measures may be included as covariate in the model.

The proportion of subjects achieving the normal range (3.2-6.1 mg/dL) will be reported. The percentage of time a subject reaches the normal range of serum phosphorus will also be summarized.

In addition, graphs showing the change of serum phosphorus over time will be provided.

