8.8.3 Secondary Efficacy Endpoints

8.8.3.1 RGI-C

The efficacy analyses evaluating RGI-C scores will be performed at Week 40 and Week 64. The GEE model will be applied to each RGI-C score type (wrist, knee, global and lower limb deformity) separately to obtain 95% CIs and p-values. Baseline RSS score will be included as a covariate in the model; age may also be included as covariate in the model.

As sensitivity analysis, t test will be performed for RGI-C scores at Week 40 and Week 64. In the case when model assumption is not met, analyses using alternative methods such as non-parametric tests will be performed.

Descriptive statistics for all RGI-C scores will be provided in both continuous and categorical summary. RGI-C responder rate will be calculated. Summary of abnormality at baseline and change in abnormality at Week 40 and Week 64 will also be presented.

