8.8.3.2 RSS

The efficacy analyses evaluating change from Baseline of RSS scores will be performed at Week 40 and Week 64. The GEE model will be applied to each RSS score type (wrist, knee and total) separately to obtain 95% CIs and p-values. Baseline RSS score and age may be included as covariate in the model. As sensitivity analysis, t test will be performed for RSS scores at Week 40 and Week 64. In the case when the model assumption is not met, analyses using alternative methods such as non-parametric tests will be performed.

Descriptive statistics for all RSS scores and change from baseline in RSS score will be provided in both continuous and categorical summary.

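### The GEE behind the main efficacy CIs and p-values names no small-sample method for about 10 children; with an uncorrected sandwich and normal reference, 5% tests run at about 9–15%.

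*SAP*

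**What the plan says.** Section 3.5 gives the number of clusters: "The study will enroll approximately 10 pediatric subjects between 1 and 4 years old, inclusive". Section 8.1 sets the error rate: "Statistical tests will be two-sided at the alpha = 0.05 significance level".

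Section 8.8.1 states that "By-visit analyses using the Generalized Estimating Equations (GEE) model will be presented for all efficacy parameters". It specifies visit as a categorical factor and an exchangeable working covariance, with independence if the model does not converge. It closes the inference with "95% confidence intervals (CIs) and p-values will be provided for statistical significance assessment".

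The endpoint sections repeat this:

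- **Serum phosphorus (8.8.2):** "The GEE model will be applied to obtain the 95% CIs and p-values", and "Baseline serum phosphorus measures may be included as covariate in the model". No other test is planned.
- **RGI-C (8.8.3.1):** GEE with baseline RSS, age optional. "As sensitivity analysis, t test will be performed for RGI-C scores at Week 40 and Week 64".
- **RSS (8.8.3.2):** GEE, baseline RSS and age optional. "As sensitivity analysis, t test will be performed for RSS scores at Week 40 and Week 64".
- **Height Z-score (8.8.3.3):** GEE; baseline Z, age and gender optional. No other test is planned.

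For RGI-C and RSS, non-parametric tests are a fallback if model assumptions fail. Appendix 1 lists GEE as the only inferential method for all four endpoints. ALP, 1,25(OH)2D and urine phosphorus are descriptive only in section 8.8.4 and Appendix 1, although the wording of 8.8.1 would take them in.

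The SAP nowhere states the standard-error type, a bias correction, a t or F reference, or degrees of freedom.

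**The concern.** The usual GEE inference, an empirical sandwich standard error referred to the normal distribution, is justified by a large number of clusters. With 10 it fails in two ways, both in the same direction. Fitted residuals are smaller than true errors, so the sandwich variance is biased downward. The cut-off of 1.96 is also smaller than the t quantile suited to so few subjects. Each subject-level covariate makes both worse, and the SAP allows up to three.

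At stake is whether intervals labelled 95% and tests labelled 5% are what they say. This includes the primary endpoint, where the GEE is the only planned inference.

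**Working it through.** The SAP gives no power calculation or operating characteristic to reproduce. The reference figure is its nominal two-sided 5%.

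**Inputs from the SAP.** n about 10 (3.5); alpha 0.05 two-sided (8.1); covariates p = 0–1 for phosphorus, 1–2 for RGI-C, 0–2 for RSS, 0–3 for height Z (8.8.2 to 8.8.3.3). Post-baseline visits to Week 40: one for RGI-C and RSS; Weeks 12, 24 and 40 for height; nine for phosphorus (the eight in section 3.2 up to Week 40, plus Week 24 from the Appendix 3 schedule).

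**Assumptions not in the SAP.** Uncorrected sandwich with normal reference; within-child correlation 0.3–0.7; normal data; complete visits; covariates centred and unrelated to outcome; the test is of zero mean at average covariate values.

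**Step 1: closed form, one visit.** With df = n − 1 − p, the uncorrected sandwich divides the residual sum of squares by n instead of df. The test therefore rejects when |t_df| > 1.96·√(df/n). The CI width relative to the correct one is 1.96·√(df/n) / t(0.975, df). A result whose exact t-based p is 0.05 is reported as 2·[1 − Φ(t(0.975, df)/√(df/n))]. For n = 10:

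| p | df | effective cut-off | correct t | true size | CI width ratio | reported p when exact p = 0.05 |
|---|---|---|---|---|---|---|
| 0 | 9 | 1.96·√0.9 = 1.859 | 2.262 | 9.6% | 0.82 | 0.017 |
| 1 | 8 | 1.96·√0.8 = 1.753 | 2.306 | 11.8% | 0.76 | 0.010 |
| 2 | 7 | 1.96·√0.7 = 1.640 | 2.365 | 14.5% | 0.69 | 0.005 |

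The p = 0 row is possible for RSS but not for RGI-C, where baseline RSS is mandatory. Simulated discrete RGI-C scores (mean of three integer ratings, bounded at 3; 10,000 replicates) gave 9.4%, 11.9% and 14.7% for p = 0, 1 and 2, against 4.8–5.1% for ordinary regression with t. Non-normality of the scale is therefore not the cause.

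**Step 2: repeated visits, simulated.** Exchangeable GEE, n = 10, null true, last visit tested, 3,000 replicates per setting, correlation 0.5. Rejection rates in %:

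| Model | sandwich + z | model-based + z | sandwich + t | Kauermann-Carroll + t | Mancl-DeRouen + t |
|---|---|---|---|---|---|
| Phosphorus, no covariate | 10.2 | 6.5 | 6.4 | 5.5 | 4.6 |
| Phosphorus, baseline | 11.1 | 6.9 | 6.8 | 5.2 | 3.6 |
| Height Z, baseline | 12.1 | 7.6 | 7.3 | 5.3 | 3.4 |
| Height Z, baseline + age + gender | 13.8 | 8.7 | 8.0 | 5.0 | 2.3 |

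Over correlations 0.3–0.7, sandwich + z gave 10.2% (phosphorus, no covariate), 11.1–11.4% (with baseline), 11.5–12.1% (height with baseline) and 13.0–15.4% (height with three covariates). CI width was 77–82% of correct for phosphorus and 65–78% for height.

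**Step 3: checks.** A separate simulation of the schedule through Week 64 (2, 4 and 11 visits; 20,000 trials per setting; correlation 0.5) gave 9.6–12.6% for RGI-C/RSS with 0–2 covariates, 9.6–13.4% for height with 0–3, and 10.0–10.7% for phosphorus with 0–1. A third run with 0–2 covariates, and 5% of visits missing in the 4- and 11-visit settings, gave 8.8–14.2%.

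**Step 4: sensitivity to n.** At correlation 0.5, sandwich + z gave 8.4–12.7% at n = 13 and 10.8–18.2% at n = 8.

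**The case against.** The strongest reply is that the SAP is silent, not wrong. It does not prescribe an uncorrected sandwich with a normal reference, so 9–15% belongs to one reading. With a model-based standard error and 1.96 the excess is smaller: 6.0–10.7% over the planned models at n = 10, and 6.5–6.9% for phosphorus at correlation 0.5. This is also an open-label, single-arm Phase 2 study with no power target, no multiplicity control and no decision tied to a p-value. RGI-C and RSS already have t tests. For phosphorus, 8.8.2 with 8.1 requires the mean, SD and SE of change at each visit, from which a reader could build a t interval.

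Much of this stands as a limit on severity. It does not remove the point. No uncorrected reading is reliably at 5%, and the reported precision depends on a choice left open in the document that is meant to fix it. The t tests are only sensitivity analyses and do not cover phosphorus or height Z-score. An interval that a reader could construct does not make the reported one correct. A large phosphorus response would probably survive correction, but its interval would still be too narrow.

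**Conclusion.** The concern holds and should be fixed. At n = 10, an uncorrected sandwich with a normal reference gives about 9–15% rejection for a nominal 5% test. The low end applies with no covariate, the high end with two or three. Confidence intervals are 18–35% too narrow. Model-based SE with z gives 6.0–10.7%, and a plain sandwich with t gives 6.0–8.9%. A t reference alone thus removes most of the excess, but not all.

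The figures are conditional on the standard-error reading and on the correlation, normality and centring assumptions listed above; the discrete-score and missing-visit checks did not change them materially. The consequence is overstated precision in the reported efficacy results, including the primary endpoint. It is not a wrong decision rule.

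**What to change.** Add to section 8.8.1: GEE inference will use a Kauermann-Carroll bias-corrected sandwich covariance and t quantiles with degrees of freedom equal to subjects minus 1 minus the number of subject-level covariates. At n = 10 this gave 4.7–5.7%. A mixed model for repeated measures with Kenward-Roger degrees of freedom is an acceptable alternative, but one method should be named. Mancl-DeRouen with t is less attractive here: it is clearly conservative, at 2.2–4.6%, and below 2% with three covariates in the 20,000-trial run.

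In addition:

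- For RGI-C and RSS at Week 40 there is one post-baseline record per child, so make ordinary ANCOVA with a t reference the main analysis.
- Extend the planned t test to serum phosphorus and height Z-score by visit (a per-visit one-sample t test ran at 5.0–5.6%).
- Fix the covariate list of each model. Sections 4.6 and 8.8.1 say baseline measures will be used, while 8.8.2, 8.8.3.2 and 8.8.3.3 make them optional. Keep the list short.
- State in 8.8.1 that ALP, 1,25(OH)2D and urine phosphorus are excluded, to agree with 8.8.4 and Appendix 1.

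**Cost.** About a paragraph of text, and no new data. Relative to uncorrected sandwich + z, reported intervals become about 22–29% wider for phosphorus, about 32% (1/0.76) to 45% (1/0.69) wider for RGI-C at Week 40, and up to about 50% wider for height Z with three covariates. If only 8 children are analysed with three covariates, Kauermann-Carroll with t becomes conservative (3.0%), a further reason to limit covariates.

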3.3 Blinding and Randomization Methods

The UX023-CL205 is an open-label Phase 2 study; all subjects will receive same starting dose Q2W. Blinding or randomization methods are not applicable for this study.

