4.6 Covariate(s)

Baseline measures will be used as covariates. For example, baseline RSS score will be used in the modeling for change in baseline in RSS score and for RGI-C score. Age and gender may also be used as covariates in growth endpoint models.

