8.8.3.3 Growth

Growth in standing height/recumbent length and weight will be summarized over time in observed value, Z-score and percentile. Individual subject growth curves will be plotted with CDC growth charts as reference. Historical growth records may be used to evaluate change in growth velocity from pre- to post-baseline.

For standing height/recumbent length Z-score, the GEE model will be applied to obtain 95% CIs and p-values on all scheduled visits. Baseline Z score, age and gender may be included as covariate in the model.

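### Adjusting a single-arm mean change for baseline makes the GEE standard error too small for the population mean change, and the SAP is inconsistent on when to adjust

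*SAP*

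**What the plan says.** The study is open-label with one arm (SAP 3.3: "Blinding or randomization methods are not applicable for this study") and is small (SAP 3.5: "The study will enroll approximately 10 pediatric subjects between 1 and 4 years old"). Section 8.8.1 applies a by-visit GEE to all efficacy parameters, with visit as a categorical term and an exchangeable working covariance, and continues: "p-values will be provided for statistical significance assessment. Baseline measures will be used as covariates". Section 4.6 gives the example that "baseline RSS score will be used in the modeling for change in baseline in RSS score and for RGI-C score".

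The endpoint sections do not agree with that general rule:

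- RGI-C (8.8.3.1) is firm: "Baseline RSS score will be included as a covariate in the model".
- Serum phosphorus, the primary endpoint (8.8.2), is optional: "Baseline serum phosphorus measures may be included as covariate in the model".
- RSS (8.8.3.2) is optional: "Baseline RSS score and age may be included as covariate in the model".
- Height Z-score (8.8.3.3) is optional: "Baseline Z score, age and gender may be included as covariate in the model".

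For RGI-C and RSS a t test at Weeks 40 and 64 is planned as a sensitivity analysis. For phosphorus, 8.8.2 names the GEE as the only source of intervals and p-values, beside descriptive statistics. The SAP does not say at which baseline value an adjusted mean is evaluated.

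**The concern.** In a randomised comparison, baseline adjustment removes noise from a difference between arms, and the overall average baseline cancels. With one arm there is nothing for it to cancel against. The adjusted mean change is then the same number as the raw mean change, reported with a smaller standard error. The gain in precision is not real if the target is the mean change in children with XLH, because the average baseline of about 10 children is itself a random quantity. The intervals would be too narrow and the p-values too small. The mixed *will* and *may* wording also leaves it open, in an open-label study, whether the narrower interval is used for phosphorus and RSS.

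**Working it through.** **Inputs.** From the SAP: one arm, about 10 children, two-sided 5% tests with 95% intervals (8.1), exchangeable GEE with visit terms and a baseline covariate (8.8.1). The SAP states no SD, correlation or power figure, so there is no planned figure to reproduce. Every correlation and SD below is an assumption.

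**Algebra.** Write a child's change as d = mu + beta(x - mean of x) + e, with x the baseline covariate. The sample mean change has true variance

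Var(d)/n = [beta^2 Var(x) + Var(e)]/n.

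With complete data, the adjusted mean at the sample-average baseline equals the sample mean change. The model (or sandwich) variance holds that average fixed and reports only Var(e)/n. Since beta^2 Var(x) = r^2 Var(d),

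reported SE / true SE = sqrt(1 - r^2), free of n,

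and the large-sample size of a nominal 5% test is 2[1 - Phi(1.96 sqrt(1 - r^2))]. For RGI-C, r is the correlation of the score with baseline RSS.

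| \|r\| | SE ratio | Size of nominal 5% test |
|---|---|---|
| 0 | 1.000 | 5.0% |
| 0.3 | 0.954 | 6.2% |
| 0.5 | 0.866 | 9.0% |
| 0.7 | 0.714 | 16.2% |

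**What r might be.** If baseline and follow-up have equal SDs and within-child correlation c, then r = -sqrt((1 - c)/2). So c = 0.5 gives r = -0.50 (9.0%), c = 0.7 gives -0.39 (7.1%), and c = 0.9 gives -0.22 (5.6%). RSS may be more extreme, because healing moves scores towards 0. Assume SDs of 1.4 at baseline and 0.7 later, with correlation 0.4:

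- Var(d) = 1.96 + 0.49 - 2(0.4)(1.4)(0.7) = 1.666
- Var(e) = 0.49(1 - 0.16) = 0.4116
- SE ratio = sqrt(0.4116/1.666) = 0.50, and size about 33%.

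**Simulation under no true change.** Two visits, exchangeable GEE, sandwich SE, normal quantile, between-visit residual correlation 0.5; 1,500 replicates (500 at n = 1000).

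| n | r | Reported/true SE, adjusted | Size, adjusted GEE | Size, visit-only GEE | Size, t test |
|---|---|---|---|---|---|
| 10 | 0 | 0.93 | 10.9% | 9.5% | 4.8% |
| 10 | -0.5 | 0.78 | 16.3% | 10.1% | 5.1% |
| 10 | -0.7 | 0.64 | 23.3% | 10.1% | 5.7% |
| 200 | -0.5 | 0.87 | 8.9% | 5.5% | 5.2% |
| 200 | -0.7 | 0.71 | 17.0% | 4.9% | 4.7% |
| 1000 | -0.5 | 0.88 | 8.4% | 4.8% | 4.8% |
| 1000 | -0.7 | 0.71 | 16.4% | 5.6% | 5.6% |

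Adjusted and raw means agreed to about 1e-14 in every run. With 11 visits and n = 10 (800 replicates), the adjusted GEE had size 15.4% at r = -0.5 and 22.3% at r = -0.7.

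**Separating two effects.** At n = 10 even the visit-only GEE runs at about 10%: its sandwich divides by n, so its size is P(|t9| > 1.96 sqrt(0.9)) = 9.6%. That is the ordinary small-sample problem. A small-sample correction does not cure the covariate problem. In the RSS-like case, with a bias-reduced SE and a t reference, interval coverage was 75% with the covariate and 97% without at n = 10, and 68% against 95% at n = 100.

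**The case against.** Several points on the other side stand.

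- *The adjusted SE is valid for another question.* It describes the mean change at the observed average baseline. That is true, but the SAP declares no such conditional target; its endpoint is the change from baseline.
- *For phosphorus and RSS the covariate is only optional.* This stands against 8.8.2 and 8.8.3.2, but 4.6 and 8.8.1 say the opposite, and for RGI-C all sections are firm.
- *Unadjusted results will be shown anyway.* Largely so for RSS and RGI-C, through the t tests. For phosphorus, the descriptive summaries give an unadjusted SE (8.1) but no planned unadjusted test.
- *The covariate can carry information when visits are missing.* This stands. With one of 10 children missing at Week 64 and r = -0.7, adjusted and raw means differed by about 0.08 SD.
- *No stated decision rule hangs on these p-values.* True: the SAP gives no power or success threshold.

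Two stronger readings are tempting and are not supported. A reader might infer that the adjustment counts regression to the mean as drug effect. It cannot, since it leaves the estimate unchanged; regression to the mean affects the raw single-arm change equally. A reader might also infer that the coefficient for a child with baseline 0 would be reported as the effect. Nothing in 8.8 says so.

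**Conclusion.** The concern holds as a defect of precision, not of bias. If the covariate is used and the mean is evaluated at the sample-average baseline with complete data, the standard error for the population mean change is short by sqrt(1 - r^2) at any sample size. The assumed |r| of 0.3 to 0.7 puts a nominal 5% test at about 6% to 16% in large samples. The effect is likely largest for RSS, and there is none at r = 0. None of these sizes can be read from the SAP as this trial's actual error rate, and a large treatment effect could remain significant either way. The exposure is greatest for phosphorus, which lacks an unadjusted test. The *will*/*may* conflict needs resolving whatever r is. No calculation was made for height Z-score or for the age and gender covariates, so the sizes do not extend to them.

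**What to change.** In 4.6, 8.8.1, 8.8.2, 8.8.3.1 and 8.8.3.2, state one rule:

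1. Reference intervals and p-values for mean change and mean RGI-C come from an unadjusted analysis. This is either the one-sample t test by visit (already planned for RGI-C and RSS, to be added for phosphorus), or a visit-only GEE with a small-sample-corrected SE and a t reference. Dropping the covariate alone is not enough, since the ordinary sandwich with a normal quantile still has about 10% size at n = 10.
2. If a baseline-adjusted GEE is kept, for example because of missing visits, say that the mean is evaluated at the sample-average baseline, add beta^2 Var(baseline)/n to its variance, and label it supportive.
3. Replace the conflicting *will* and *may* sentences with this rule.

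Two apparent alternatives should be avoided. Centring at a fixed prespecified baseline changes what is estimated. Treating baseline as a first repeated response cannot work for RGI-C, which is itself a rating of change.

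The cost is SAP wording and little code. Intervals become somewhat wider, and the unadjusted mean does not use baseline to allow for children missing at later visits.
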